3.6 Evaluation of Toxicity

Nurses or research members will evaluate for symptoms of muscle fatigue, numbness, tingling, or pain of stimulated extremity. Prolonged nerve stimulation could theoretically result in tetanic muscle contraction and nerve damage, though this has not been reported in the literature. Rare contact dermatitis has been reported to electrode gel. Adverse events will be captured. The symptoms assessed using the Evaluation of Toxicity will be considered an adverse event if graded 4 or above on a 0 to 10 scale.

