3.1 Patient Eligibility

Inclusion criteria:

1. Adults at least 18 years of age
2. Female gender
3. History of patient reported PONV, CINV or motion sickness
4. Patients scheduled for Breast Surgery
5. Sign an informed consent indicating they are aware of the investigational nature of this study.

Exclusion criteria:

1. Patients scheduled for paravertebral block
2. Upper extremity deformity contralateral to the site of disease that could interfere with accurate point location or alter the energy pathway as defined by traditional acupuncture theory
3. Local skin infections at or near the acustimulation site
4. Pre-existing nausea and vomiting, defined as nausea or vomiting requiring pharmacological treatment greater than 3 times in the week preceding screening
5. History of CVA or other central nervous system disorder resulting in residual weakness or paresis of

- extremity contralateral to the site of disease
- 6. Grade III or IV upper extremity peripheral neuropathy
- 7. Cardiac pacemakers. Patients involved in this protocol will receive electrical stimulation. For safety reasons, electrical stimulation should be avoided in patients with pacemakers
- 8. Metal implants to the treatment extremity. For safety reasons, use of electrical stimulation should be avoided
- 9. Current acknowledged use of any illicit drugs, medical marijuana (including Marinol), or evidence of alcohol abuse as defined by The American Psychiatric Association criteria [41]. This includes patients who are currently in the recovery process.
- 10. Pregnancy as this would alter anesthesia plan
- 11. Bowel obstruction
- 12. Surgery that would not allow access to at least one P6 site.

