3.3 Treatment Plan

The experimental group will receive anesthesiologist-provided intraoperative NMBM electrical stimulation of P6 combined with prophylactic anti-emetics, while the control group will only receive prophylactic anti-emetics.

Recruitment and registration

This study will be conducted at the University of Texas MD Anderson Cancer Center (MDACC). Patients will be identified from the breast surgery schedule. An initial screen will be conducted by the research staff member via telephone or in person for history of PONV, CINV, or motion sickness. Completion screening and consent will then take place prior to surgery, and will again be conducted by the research staff. Data collection will be completed by the participant either electronically or using paper and pencil. The electronic data collection will be done via File Maker Pro which is a HIPPA and MD Anderson approved system.

Randomization

Prior to surgery and after baseline data collection, all participants will be randomized into treatment or control groups using a form of adaptive randomization called minimization[42] for a better group balance based on participant characteristics that might be related to outcome. The factors used in the minimization will include smoking status (never smoker, former smoker, current smoker), history of PONV, prior PONV (Yes/No/Unknown), history of CINV (Yes/No/Unknown), history of motion sickness (Yes/No), and anticipated duration of surgery (running median)). We will use a deterministic probability of 0.99 in the minimization algorithm given the small sample sizes. Randomization will be completed through FileMaker Pro database. Patients and PONV evaluators will be blinded to group assignments. The attending anesthesiologist will not be blinded to group assignment as they will perform the intervention but will not be involved in PONV assessment.

Acupoint stimulation procedure

Control group: Patients in the control group will have pads placed on at P6 and SJ5 on the contralateral arm

induction, however, electrical stimulation will not be given.

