All patients will receive standard prophylactic antiemetics consisting of Zofran 4 mg IV x1, Dexamethasone 10 mg IV x 1, Phenergan 6.25 mg IV x 1, and Pepcid 10mg x 1 intraoperatively as noted above. Rescue treatment for PONV will be according to our standard post-operative algorithm, i.e. for PONV occurring less than 4 hours following PACU arrival: Granisetron 1 mg IV x 1. If ineffective, this can be followed by Promethazine 6.25 mg IV up to 2 doses, after which the PACU attending is called for further intervention. For PONV occurring greater than 4 hours following PACU arrival, Ondansetron 4 mg IV can be given for two doses.

Assessment

Assessment of PONV and Pain will be conducted by the PACU nurse or research member. Per PACU procedures, the nurse will also determine when the patient is ready for PACU discharge. This nurse or research member will be blinded to group assignment.

Anesthesiologist training

P6 NBMN stimulation will be performed by a team of 4 MDACC anesthesiology faculty members. Each member has experience in using NBMN stimulation. Each participant will have training in P6 and SJ5 acupoint location with a licensed acupuncturist ([name]) and will be observed placing NBMN monitor on appropriate acupoints.

3.4 Pretreatment evaluation: Prior to beginning treatment, the following will be provided/obtained:

- a. Review of the nature and purpose of the study with potential subjects and verification that the patient meets all eligibility criteria.
- b. Written informed consent from patients who agree to participate in the study prior to any study procedures.

- c. Complete history and physical examination of eligible subjects.
- d. Review and documentation on the worksheet of specific medical history information including type of malignancy and previous surgical history.
- e. Documentation of all medications taken by the patient in the preceding 30 days.
- f. Review of the patient's available medical record to ensure that inclusion and exclusion criteria have been met.
- g. Smoking status as stated in electronic medical record.
- h. Acupuncture Expectancy Scale (AES). This 4-item instrument will be administered at time of consent.

3.5 Measurement of effects:

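### Limb symptoms become adverse events at a fixed score of 4 with no pre-operative rating to set them against, and the toxicity questions have no fixed time relative to the blinded nausea ratings

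*Combined protocol and SAP*

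**What the plan says.** Section 3.6 (Evaluation of Toxicity) provides that "Nurses or research members will evaluate for symptoms of muscle fatigue, numbness, tingling, or pain of stimulated extremity". A symptom "will be considered an adverse event if graded 4 or above on a 0 to 10 scale". The section gives no time point, no number of ratings and no reference to a pre-operative score.

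Section 3.4 (Pretreatment evaluation, items a to h) includes "Complete history and physical examination of eligible subjects" and a record review, but no 0-10 rating of limb symptoms.

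Section 3.1 requires "History of patient reported PONV, CINV or motion sickness", any one of which is enough. Its neuropathy exclusion is limited to "Grade III or IV upper extremity peripheral neuropathy".

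Section 3.3 (Assessment) says "Assessment of PONV and Pain will be conducted by the PACU nurse or research member", and adds "This nurse or research member will be blinded to group assignment". Section 3.5 schedules the nausea and pain ratings every 15 minutes in the PACU. Controls have pads at the same two points but receive no current (section 3.3).

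Section 3.8 compares adverse events between study groups and sends aggregate safety data to the DSMB, which may consider stopping for toxicity.

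**The concern.** The cut-off of 4 is absolute. A woman with long-standing Grade II neuropathy who would have scored her numbness 5 on the morning of surgery scores 5 in the PACU and becomes an adverse event, whichever group she is in. Such women can enter: CINV history is one route into the trial and implies past chemotherapy, and Grade I-II neuropathy is not excluded. Section 3.6 itself names nerve damage as the theoretical harm, and its symptoms are those that existing neuropathy produces.

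Two matters of wording add to this. First, a question about the stimulated limb has no literal meaning for a control. If controls are not asked, the comparison is one-sided and the person asking must know the allocation. Second, nothing keeps the toxicity questions apart from the repeated nausea ratings, and both tasks fall to nurses or research members. Nausea is the patient's own score and feeds the primary endpoint, so a question about tingling in the limb, or the answer to it, could cue the patient or the assessor.

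**Working it through.** **Plan's own figure.** Inputs from section 3.8: PONV 0.40 and 0.25, one-sided alpha 0.1, power 80%. With pooled variance and no continuity correction,

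n = [1.2816 × √(2 × 0.325 × 0.675) + 0.8416 × √(0.40 × 0.60 + 0.25 × 0.75)]² / 0.15² = 87.01, rounded up to 88 per group.

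The stated 88 is reproduced (power 80.3%). This point does not dispute it.

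**Adverse event counts.** The documents give neither a background symptom rate nor a stimulation effect, so both are assumed. Let b be the share of women whose score is already 4 or more before surgery and stays there. Let 8% of the remaining women reach 4 or more because of stimulation, and none because of pads alone.

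- Recorded rate, stimulation group: pE = b + (1 − b) × 0.08
- Recorded rate, control group: pC = b
- 90% CI half-width of the difference: 1.645 × √{[pE(1 − pE) + pC(1 − pC)] / 88}

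| b | pE | pC | Expected events of 88 (stimulation vs control) | Difference ± half-width (points) |
|---|---|---|---|---|
| 0 | 0.080 | 0 | 7.0 vs 0 | 8.0 ± 4.8 |
| 0.05 | 0.126 | 0.05 | 11.1 vs 4.4 | 7.6 ± 7.0 |
| 0.10 | 0.172 | 0.10 | 15.1 vs 8.8 | 7.2 ± 8.5 |
| 0.20 | 0.264 | 0.20 | 23.2 vs 17.6 | 6.4 ± 10.4 |

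The expected difference shrinks a little. The interval widens much more, and by 10% background an interval centred on a real excess includes zero. At 10%, the total rises from 7.0 to 15.1 + 8.8 = 23.9 events, most of them unrelated to stimulation.

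**Effect of a baseline.** If stable prior symptoms are not counted, the 10% row becomes (1 − 0.10) × 0.08 = 7.2% vs 0%, with half-width 1.645 × √(0.072 × 0.928 / 88) = 4.5 points instead of 8.5. This supposes that women with stable symptoms repeat their earlier score. A one-point drift upward from 4 or more would still count.

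**Cueing.** Take true PONV as 40% in both groups and let cueing lower recorded PONV in the stimulation group by e. The rejection probability of the planned test is Φ[(e − 1.2816 × SE0) / SE1], where SE0 is the pooled and SE1 the unpooled standard error with 88 per group. For e of 2, 4 and 6 points it is about 16%, 23% and 32%, against a nominal 10%. The documents give no value for e. For scale, if every PONV record were suppressed among the 8% with a new score of 4 or more, e would be 0.08 × 0.40 = 3.2 points. Milder symptoms could add to that.

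**The case against.** The strongest reply is that a randomized, pad-only control group exists to measure background symptoms. CINV history is also a minimization factor ("history of CINV (Yes/No/Unknown"), so prior symptoms should be roughly balanced. This stands as far as bias is concerned. A reader might infer that the missing baseline creates a false excess of toxicity, but the table shows the expected difference staying close to 8 points. What balance does not restore is precision, the meaning of the absolute counts, or the attribution of an individual event.

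Other stronger readings also fail:

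- **That entry selects women with a chemotherapy history.** CINV is one of three alternatives; such women are admitted, not required, and their share is not given. The history, physical examination and neuropathy exclusion imply some pre-operative review of the limb, though not on the adverse event scale.
- **That the blinded PONV assessor is the person who asks the toxicity questions.** The staff categories overlap; the documents neither say nor rule out that it is the same individual.
- **That the questions unblind.** This is plausible but not documented. Both groups wear pads, current runs only under anaesthesia, and if background symptoms are common, a report is weak evidence of allocation.
- **That the group tabulation is the only safety output.** Adverse events are captured generally, and safety data also go to the DSMB.
- **That a baseline alone would catch a rise from 0 to 3.** That loss comes from the cut-off of 4, so it needs a separate report of change.

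**Conclusion.** The concern holds in a limited form. As written, the rule counts stable pre-existing limb symptoms as stimulation events in both groups. That inflates the counts compared by group and sent to the DSMB, and widens the interval around any real excess: on assumed rates of 8% new and 10% pre-existing symptoms, from ± 4.8 to ± 8.5 points. The size depends wholly on a background rate that the documents do not give, and at 0% background there is no loss. No false excess between groups is to be expected.

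The undefined limb for controls and the unfixed timing are gaps in the text. Any effect on the primary endpoint through cueing is a possibility, not a finding. The change is worth making before enrolment because a pre-operative score cannot be recovered afterwards. The sample size is unaffected.

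**What to change.** 1. Add to section 3.4 the same four 0-10 ratings (fatigue, numbness, tingling, pain) for the limb that will carry the electrodes, in all patients. In section 3.6, keep the cut-off of 4 but count an event only if the score also exceeds the pre-operative rating. In section 3.8, report change from the pre-operative rating by group, so that new symptoms below the cut-off are visible.
2. Word the post-operative item as the arm with electrodes, for both groups. Ask it after the final nausea and satisfaction ratings at PACU discharge, and record spontaneous complaints whenever they occur.

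**Cost.** About one minute per patient and a fixed order of questions at discharge. Symptoms that resolve before discharge and are not volunteered may be missed, and a fixed order cannot prevent cueing by a spontaneous complaint.

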3.7 Criteria for Removal from the Study

Subjects will be removed from the study if any of the following occur:

- a. Patient request for removal.
- b. Primary physician request for removal.
- c. Surgical complication such as infection, bleeding, organ failure, or mechanical bowel obstruction.
- d. Development of skin changes at the acustimulation sites during the period of treatment.

3.8 Statistical considerations:

Analysis Methods:

The primary aim of this study is to examine the efficacy of electrical stimulation of P6 combined with prophylactic antiemetics versus pharmacological prophylaxis alone in preventing the incidence of PONV following breast surgery in patients at high-risk for PONV. We will make a preliminary evaluation of efficacy by testing for a difference in incidence of PONV between study arms. If a subject fails to have complete control of nausea (as defined in Section 3.5) at any time during her PACU stay, she will be considered as having PONV. We will use a 1-sided chi-squared test of proportions with Type I error of 0.1 to test for difference in PONV incidence.

Secondary endpoints of interest are feasibility of the study, use of rescue anti-emetic medications, post-operative patient satisfaction, PACU length-of-stay, hospital admission, and patient expectations. We will calculate rates, frequencies, and 90% confidence intervals (CIs), as applicable, and will judge the trial feasible if at least 20% of screened patients meet inclusion criteria, 50% of patients who meet the inclusion criteria consent, and 75% of patients within the acupuncture arm complete all procedures. We will also calculate the appropriate summary statistics and 90% CIs for other secondary endpoints by group, as well as for differences between groups. We will evaluate preliminary differences in the severity of PONV and use of rescue anti-emetic medications between groups using mixed model analyses. Additionally, we will explore associations between genetic polymorphisms in COMT, 5HT3, OPRM1, and DRD2 and response to P6 stimulation using ANOVA models with factors such as the number of matching alleles and treatment group. Finally, we will tabulate and compare adverse events by study arm.

Sample size calculations:

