This study is powered for a preliminary examination of efficacy in order to determine whether there is early evidence of efficacy to justify moving forward with further studies of intra-operative NMBM stimulation of P6 to prevent PONV. Similar studies in other patient populations in which pharmacological prophylaxis was used with or without acupoint stimulation found that incidence of PONV was approximately 0.4 in the control group and 0.25 in the experimental group.[17-20] To test whether a similar difference exists in this patient population, we will need 88 patients per arm to achieve 80% power when using a 1-sided chi-squared test with $\alpha = 0.1$. With regard to the secondary objective of feasibility evaluation, to achieve a sample size of 88 per arm, assuming 20% of screened patients meet the inclusion criteria and of those patients, 50% consent, we would need to screen 1,760 potential subjects to obtain 352 eligible subjects, and of these, 176 would consent to be in the study. Under these circumstances, the half-width for a 90% confidence interval regarding inclusion criteria would be 0.016 and the half-width for a 90% confidence interval regarding consent would be 0.044. If 75% of the subjects within the acupuncture arm complete the study, the 90% confidence interval around this statistic would be 0.076 with N=88 for the acupuncture arm.

Missing Data:

Given a patient's active involvement only lasts until discharge from PACU, we do not expect to have issues with missing data and drop-outs, and our primary analyses will be based on observed data. Should we find that missing data and/or drop-outs become an issue ($> 10\%$ in either arm), we will conduct additional sensitivity analyses using approaches including multiple imputation, pattern-mixture models, and selection models to account for potential missing-at-random or missing-not-at-random mechanisms.[43] The primary along with the sensitivity analyses will provide a comprehensive assessment of the effects of interest, and similar results based on these analyses would strengthen our preliminary study findings.

Interim Analysis:

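### Contact dermatitis, the one harm the protocol says has been reported, is not among the symptoms actively evaluated, and removal for skin changes is not tied to adverse-event recording, so it could be under-counted

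*Combined protocol and SAP*

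**What the plan says.** Section 3.6 mentions two kinds of harm from the intervention. The first is mechanical or neural and is presented as hypothetical: "Prolonged nerve stimulation could theoretically result in tetanic muscle contraction and nerve damage, though this has not been reported in the literature". The second is presented as having occurred: "Rare contact dermatitis has been reported to electrode gel".

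Active evaluation is described in one sentence: "Nurses or research members will evaluate for symptoms of muscle fatigue, numbness, tingling, or pain of stimulated extremity". A general statement follows the two harms, "Adverse events will be captured", and after it a grading rule: "The symptoms assessed using the Evaluation of Toxicity will be considered an adverse event if graded 4 or above on a 0 to 10 scale".

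The skin at the pad sites appears again in section 3.7, where item (d) lists as a ground for removal from the study: "Development of skin changes at the acustimulation sites during the period of treatment".

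The safety analysis is the last sentence of Analysis Methods in section 3.8: "Finally, we will tabulate and compare adverse events by study arm". No safety population is defined. Under Interim Analysis, section 3.8 also sends aggregate safety data to the DSMB, which may consider halting enrollment for toxicity.

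Under section 3.3, women in both arms have pads at P6 and SJ5. The treatment group's electrodes are described as pre-gelled. The text does not say whether the control pads carry gel.

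**The concern.** What is solicited does not match what is known. The four evaluated symptoms relate to muscle and nerve effects, which the protocol calls theoretical. The reported harm is a visible skin reaction, and nobody is asked to check for it once the pads are off. The woman is under anaesthesia while the pads deliver stimulation, so she cannot volunteer a complaint during that time.

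The one rule that mentions skin changes leads to removal and then stops. It does not say whether the event goes on an adverse-event form or whether the woman remains in the denominator. The evaluation is also worded for the arm that receives stimulation. Controls wear pads without current, so it is unclear whether they are checked in the same way.

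At stake is whether this harm is ascertained completely, and equally in both arms, in the by-arm table and in the DSMB's toxicity review. The trial is meant to inform a larger multi-institutional study, whose planners would want a usable count. The primary endpoint, its test and the sample size are not affected.

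**Working it through.** **Step 1: set the provisions side by side.**

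| Question | Listed symptoms (3.6) | Skin reaction |
|---|---|---|
| Previously reported, according to the protocol? | Related nerve and muscle harms: no, theoretical only | Yes, rare |
| Actively evaluated? | Yes | Not listed |
| Rule for when it counts as an adverse event? | Graded 4 or above on 0 to 10 | None stated |
| Covered by the general capture sentence? | Yes | Yes, if someone observes or reports it |
| Consequence named elsewhere? | None | Removal under 3.7(d) if it develops during treatment |
| Kept in the by-arm table after removal? | Not stated | Not stated |

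A skin reaction thus has two routes. If it is noticed during treatment, 3.7(d) applies, and recording it as an adverse event is left to the general sentence. If it appears after treatment but before PACU discharge, 3.7(d) does not apply and the general sentence is the only route. Neither route prompts a recorded skin check.

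**Step 2: the arm size used for scale.** Inputs from section 3.8: PONV 0.40 against 0.25, one-sided alpha 0.1, power 80%. With pooled variance and no continuity correction, the mean proportion is 0.325 and

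n = [1.2816 × √(2 × 0.325 × 0.675) + 0.8416 × √(0.40 × 0.60 + 0.25 × 0.75)]² / 0.15² = 87.006, rounded up to 88 per arm.

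This reproduces the plan's figure. It serves here only as the number of women in one arm.

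**Step 3: how many cases could there be?** The documents give no dermatitis rate, so p is assumed over a range. Expected cases are 88p, and the chance of at least one is 1 − (1 − p)^88.

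| Assumed p | Expected cases in 88 | Chance of at least one |
|---|---|---|
| 0.1% | 0.09 | 8% |
| 0.5% | 0.44 | 36% |
| 1% | 0.88 | 59% |
| 2% | 1.76 | 83% |

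If the control pads are also gelled, the exposed number is 176. The chance of at least one case, 1 − (1 − p)^176, becomes 16%, 59%, 83% and 97%.

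**Step 4: how fragile is such a row?** At p = 1%, the chance of exactly one case in 88 is 88 × 0.01 × 0.99^87 = 0.367, and of exactly two is 3,828 × 0.01² × 0.99^86 = 0.161. Of the 0.587 chance of any case, (0.367 + 0.161) / 0.587 = 90% is one or two cases. At p = 2% the same calculation gives (0.304 + 0.269) / 0.831 = 69%. When any case occurs at these rates, the usual count is one or two, and failing to record those women would leave the row at zero.

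**The case against.** The best reply is that the general capture sentence is unrestricted and comes straight after the dermatitis sentence. A reaction that anyone sees can be recorded under it. Applying 3.7(d) presupposes that someone sees the skin, and section 3.3 has staff clean residual gel from the sites. This stands, and it is why omission is only possible. It does not supply a prompt, a time or a form entry.

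Four stronger readings are tempting and are not supported:

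- A reader might infer that an adverse event exists only at grade 4 or above, which would shut out dermatitis. The threshold applies only to the symptoms assessed in the toxicity evaluation. A skin reaction faces no such hurdle; it simply has no counting rule.
- A reader might infer that removed women disappear from the safety table. No text deletes their events, and section 3.8 tabulates by arm without exclusions. The documents are silent on the point.
- A reader might infer that the by-arm table is the trial's only safety output. Safety data also go to the DSMB. That output draws on the same records, so it does not cure under-recording.
- A reader might argue that an empty row, 0/88, has a one-sided 95% upper limit of 1 − 0.05^(1/88) = 3.3% and would wrongly exclude a true rate of 5%. That needs a rate hard to call rare and the loss of every one of 88 × 0.05 = 4.4 expected cases. If removed women were dropped, the denominator would also fall below 88.

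Reactions or persistent numbness after PACU discharge are a separate matter. Section 3.8 says "Given a patient's active involvement only lasts until discharge from PACU", but it does so when discussing missing data. Section 3.6 sets no safety window, and the documents describe no later visits from which such events could be abstracted.

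It can also be said that bias between the arms is not shown. That is correct: if both arms wear gelled pads, under-recording could affect both. The point concerns ascertainment, with unequal checking as an open possibility.

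**Conclusion.** The concern holds in a limited form. The only harm described as reported is left to unsolicited capture, and the one provision that mentions it does not connect removal with recording or counting. Followed literally, the plan could under-count skin reactions in the by-arm table and in the DSMB's safety data. It does not make that certain, and it does not show that the table will look better than the truth.

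The size is small in absolute terms: about 0.09 to 1.8 expected cases in 88 women at assumed rates of 0.1% to 2%. Those rates are assumptions, chosen because the protocol says only that the event is rare. Small expected counts make each record matter, because one or two missing entries can turn an observed harm into none. The correction is worth making because it is cheap and uses staff already in place.

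**What to change.** Make three changes to recording and counting.

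1. Add to the section 3.6 evaluation one present/absent item for a skin reaction at either pad site. The nurse or research member already doing the evaluation completes it at PACU discharge, in both arms, with a short description or severity.
2. State that any skin change noted under 3.7(d) is recorded as an adverse event.
3. State in section 3.8 that adverse events are tabulated by arm for all women who had pads placed, including any removed under 3.7.

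The removal criterion itself is a clinical rule and stays as it is.

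The cost is one form line and two sentences, with no added visit, staff or procedure. The drawback is that some minor pad marks will be counted. The description or severity recorded with the item lets the analysis separate them from dermatitis.

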No formal interim analyses are planned, however, we will present aggregate efficacy and safety data to the MDACC DSMB so that they can assess whether enrollment should halt for futility or toxicity reasons. In addition to summary statistics, we will also calculate $\Pr[\pi_{IES} < \pi_{SOC} \mid \text{data}]$, where π_{IES} and π_{SOC} are the proportions of women who report complete control of nausea (as defined in Section 3.5 of the protocol) at any time during the PACU stay in the electrical stimulation arm and control arm, respectively. This probability will

also be presented in the DSMB report to assess whether enrollment should continue in the trial. When calculating this probability, we will assume that both π_{IES} and π_{SOC} have a prior beta distribution with $\alpha = 0.8$ and $\beta = 1.2$. In addition, we will examine the defined feasibility criteria during the annual DSMB report. If the results look sufficiently clear that feasibility is not achieved, we will consider terminating the study, provided that the DSMB recommends so.

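### Limb symptoms are graded 0–10 but compared between arms only as events at 4 or above, so an excess of mild symptoms (1–3) from stimulation would go uncompared

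*Combined protocol and SAP*

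**What the plan says.** Section 3.6 (Evaluation of Toxicity) names the symptoms: "Nurses or research members will evaluate for symptoms of muscle fatigue, numbness, tingling, or pain of stimulated extremity". It then sets the rule that such a symptom "will be considered an adverse event if graded 4 or above on a 0 to 10 scale". The same section states "Adverse events will be captured", with no numeric threshold for events outside the graded symptoms.

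Section 3.8 (Analysis Methods) gives one between-arm toxicity analysis: "Finally, we will tabulate and compare adverse events by study arm". It names no test, interval or level for this.

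Two other statements in section 3.8 might have covered the grades but do not say so:
- "We will also calculate the appropriate summary statistics and 90% CIs for other secondary endpoints by group". Toxicity is not in the list of secondary endpoints to which this applies.
- Under Interim Analysis, "we will present aggregate efficacy and safety data to the MDACC DSMB". No analysis of symptom grades is described there.

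**The concern.** A cut at 4 can serve as a reporting threshold. Here it is also the only form in which local toxicity is compared between arms, and the documents give no reason for choosing 4. Grades of 1–3 are collected and then enter no stated comparison.

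The trial is meant to inform a larger multi-institutional study, and stimulation runs throughout surgery. If stimulation mainly produces mild tingling, numbness or fatigue, the report could show no difference in adverse events although the two grade distributions differ. Grades may also be lowered by opioids given during anesthesia, which would push symptoms below the cut. By contrast, PONV is reduced to yes/no for the primary endpoint, but its severity gets a separate mixed-model analysis in section 3.8.

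**Working it through.** **1. The plan's own figure.** The only sample size in section 3.8 is for PONV: "We will use a 1-sided chi-squared test of proportions with Type I error of 0.1", with "incidence of PONV was approximately 0.4 in the control group and 0.25 in the experimental group". Pooled-variance formula, no continuity correction, mean proportion 0.325:

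n = [1.2816·√(2·0.325·0.675) + 0.8416·√(0.40·0.60 + 0.25·0.75)]² / 0.15² = (0.8489 + 0.5503)² / 0.0225 = 87.01, rounded up to 88.

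Power at 88 per arm is 80.3%. The figure reproduces, but it concerns efficacy. The plan states no power for toxicity.

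**2. Inputs for toxicity.** From the documents: 88 per arm, grades 0–10, cut at 4, 1-sided 0.1 for the primary test. Assumed: every symptom rate below. Each symptom is grouped as 0 / 1–3 / 4+.

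**3. Proportional-odds shifts.** For a control probability p of reaching a boundary, the stimulated probability is OR·p / (1 − p + OR·p). Example, control 85/10/5 with OR 2: at 1 or above, 0.30/1.15 = 0.261; at 4 or above, 0.10/1.05 = 0.095. The stimulated arm is therefore 73.9/16.6/9.5.

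The tie-corrected rank-sum z on three categories was compared with the same statistic split at 4, over 40,000 simulated trials per row. Power in %, grades vs cut:

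| Control % at 0 / 1–3 / 4+ | OR | 1-sided 0.1 | 1-sided 2.5% |
|---|---|---|---|
| 90/7/3 | 2 | 62 vs 38 | 34 vs 12 |
| 90/7/3 | 3 | 92 vs 64 | 76 vs 32 |
| 85/10/5 | 2 | 72 vs 46 | 45 vs 20 |
| 85/10/5 | 3 | 97 vs 77 | 87 vs 52 |
| 75/15/10 | 2 | 82 vs 61 | 59 vs 35 |
| 75/15/10 | 3 | 99 vs 92 | 95 vs 75 |
| 60/25/15 | 2 | 87 vs 71 | 67 vs 44 |
| 60/25/15 | 3 | 99.5 vs 96.6 | 97 vs 87 |
| 90/3/7 | 2 | 62 vs 53 | 34 vs 27 |
| 90/3/7 | 3 | 92 vs 85 | 76 vs 64 |

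The gain from using the grades is about 3 to 28 points at 1-sided 0.1 and about 7 to 44 at 1-sided 2.5%.

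**4. Shifts in one band only.** Same test:

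| Pattern (% at 1–3 / 4+), control → stimulated | 1-sided 0.1 | 1-sided 2.5% |
|---|---|---|
| Mild only: 10/2 → 30/2 | 97 vs 12 | 89 vs 2 |
| 4+ only: 10/2 → 10/12 | 75 vs 94 | 49 vs 78 |
| 4+ only, more mild background: 30/2 → 30/12 | 69 vs 94 | 42 vs 78 |

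In the mild-only row the rate at 4+ is 2% in both arms, so the cut rejects only at about its false-positive rate. In the 4+ rows the ordering reverses and the cut is the better analysis.

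**The case against.** The strongest reply is that section 3.8 describes ordinary descriptive safety reporting. The study is powered for preliminary efficacy, no toxicity hypothesis or test is named, and toxicity is not a listed secondary endpoint, so there is no planned power to lose. This stands, and it limits the point to a gap in the planned comparison.

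A reader might infer that the cut throws away most of the power to see local harm. The documents do not support that:
- They give no symptom rates.
- The proportional-odds pattern favours a rank test by construction. Even so, power falls by more than half in only three of the ten rows at 1-sided 2.5% (90/7/3 at both ORs, 85/10/5 at OR 2) and in none at 1-sided 0.1.
- If the excess lies only at 4 or above, the cut does better. The theoretical harms that section 3.6 names, tetanic contraction and nerve damage, need not appear as mild grades.

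It can also be said that the text does not forbid tabulating grades, and that toxicity is not singled out, since the 0–10 pain score has no named analysis in section 3.8 either. Both are true. But silence leaves the choice until after the data are seen, and the one comparison that is specified uses events.

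**Conclusion.** The point holds as a gap in the analysis plan. As written, grades 1–3 enter no stated between-arm comparison, and an excess confined to them would be almost invisible.

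The size is not fixed by the documents. Across the assumed patterns, at 1-sided 0.1, the difference in power (grades minus cut) runs from 97 − 12 = 85 points in favour of the grades to 94 − 69 = 25 points in favour of the cut. It is 3 to 28 points in favour of the grades under proportional odds. These figures rest on 88 evaluable patients per arm, one symptom at a time, and invented symptom rates. Neither analysis covers both patterns, so the grade comparison should be added to the event comparison and should not replace it. This is an inexpensive improvement to the safety analysis. It does not affect the primary efficacy conclusion.

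**What to change.** Keep 4 or above as the adverse-event threshold and keep the comparison of adverse events. Add to section 3.8:

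> For each symptom in section 3.6, the worst 0–10 score on the electrode arm (both groups) will be tabulated by study arm as 0, 1–3 and 4 or above, and the difference between arms will be estimated with a rank-based or proportional-odds analysis and a 90% CI, as exploratory safety analyses without multiplicity adjustment.

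The words on the electrode arm matter because section 3.6 speaks of the stimulated limb, while controls have pads but no stimulation. The same limb must be graded in both groups.

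Cost: one sentence and four extra exploratory comparisons, with no new patients, visits or procedures, provided the numeric grade is recorded and not only the event. Mild symptoms unrelated to stimulation, such as from an IV line or positioning, will also be counted. They should arise about equally in both arms, and they add noise.
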